#### **8.2.8.2 Injected and Non-injected Lesions**

To explore the treatment effect of IMO-2125 between the measurable injected and non-injected lesions, the sum of the longest diameters will be calculated separately among the injected lesions and the non-injected lesions for each subject at each nominal visit in the combination treatment arm (ipilimumab with IMO-2125). Due to the potentially different numbers of injected and non-injected lesions involved in the calculation for each subject, the percent reduction from baseline in the sum of the longest diameters will be used for the analysis. For each subject, the paired difference in the percent reduction between the injected and non-injected lesions will be calculated. Any measurable new lesions noted post-baseline will be excluded from the calculation.

#### **8.2.9 Other Assessments**

All data will be reported according to the nominal visit for which it was reported (that is, no visit windows will be applied during dataset creation). Unscheduled data will only be included in summaries of worst-case (highest and/or lowest) post-baseline assessments.

If multiple safety assessments on different days are reported for the same scheduled assessment, then the latest assessment for that scheduled assessment will be analyzed.

If multiple assessments are reported on the same date for the same scheduled planned time, then the worst-case result will be analyzed.

Data from all assessments (scheduled and unscheduled), including multiple assessments, will be included in listings.

Idera Pharmaceuticals, Inc.  
 Statistical Analysis Plan  
 Protocol Number: 2125-MEL-301

---

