9.3.4. Dose Modification

The most common AEs following intratumoral administration of IMO-2125 have been non-specific “flu-like” symptoms and mild to moderate injection site reactions. In combination with ipilimumab, IMO-2125 has been associated with irAEs (Section 10.1.3.4) and fever. Ipilimumab dosing will follow the local package insert. IMO-2125 therapy should be continued if ipilimumab is discontinued early for toxicity.

Dose modification instructions for IMO-2125 including its use in combination with ipilimumab are provided in [Table 3](#).

Table 3: Dose Modification Instructions for IMO-2125

Event	Action	Dose Modification
Local or mild systemic reaction (e.g., pyrexia)	Supportive measures as required. Continue treatment with IMO-2125 per clinical discretion.	None
Severe systemic reaction for which more aggressive measures including hospitalization are required (e.g., severe hypotension)	Supportive measures as required. Hold further dosing until the event resolves to baseline or Grade 1 and the re-treatment criteria below are met.	None.
Life-threatening AE (e.g., anaphylaxis)	Supportive measures as required.	Discontinue treatment
Serious procedural complication related to deep or visceral injection (e.g. pneumothorax or hematoma formation)	Supportive measures as required	Discontinue visceral injections (treatment may be continued if a superficial lesion or tumor-involved lymph node is available for injection instead)

Conventional supportive medications (including infliximab for immune-related colitis and growth factor support) are permitted.

Criteria for re-initiation of treatment with each dose of study drug include:

- ANC $\geq 1.5 \times 10^9/L$ (1500/ μL);
- Platelets $\geq 75 \times 10^9/L$ (75,000/ μL);
- Resolution of all clinically significant non-hematologic toxicities for which a causal association to study treatment cannot be ruled out to Grade ≤ 1 or baseline.

If the subject does not meet these criteria, dosing will be delayed, and the subject should be re-evaluated within 48 to 72 hours. If the next dose is delayed by more than 21 days for toxicity, the subject should be removed from study treatment unless approved by the medical monitor.

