9.3.4.2. Procedures for Assessment of Subjects with Changes in Complement Levels

Activation of complement in non-human primates is a well-described effect of phosphorothioate oligonucleotides, including IMO-2125. Monkeys are thought to be particularly sensitive to oligonucleotide-induced complement activation and a similar direct oligonucleotide-induced complement activation has not been observed in humans or other species.

Complement samples will be collected at Weeks 1 and 14 for Arm A and Weeks 1 and 11 for Arm B, according to the Schedule of Events table (see [Table 1](#)), and will be analyzed at a central laboratory (Medpace Reference Laboratories). If at any time during study participation, a subject experiences an acute drop in complement (total hemolytic complement assay, complement component 3, or complement component 4) levels $\geq 50\%$ or a drop to an absolute value below the lower limit of normal with reference to baseline testing or most recent values on study, the Sponsor will notify the site and the following procedures should be performed by the investigator:

1. Perform a safety evaluation and any necessary testing for the subject as clinically indicated.
2. If the results of the safety evaluations suggest any safety concerns associated with the drop in complement levels, hold the study drug treatment.
3. The patients should return to the clinic to have another serum sample drawn and sent to the central laboratory to confirm decreased complement levels.

Based on the results of this work-up and the subject’s disease assessment/response to study drug, the Investigator, in discussion with the Sponsor’s Medical Monitor, will determine the subject’s risk/benefit profile and discuss appropriate next steps regarding the subject’s continued treatment with study drug.

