### **11.8 CLINICAL LABORATORY EVALUATIONS**

The laboratory tests in [Section 12.2](#) of the protocol, Laboratory Assessments, will be summarized as described in this section.

Idera Pharmaceuticals, Inc.  
 Statistical Analysis Plan  
 Protocol Number: 2125-MEL-301

Category	Analyte
Hematology	CBC: white blood cell (WBC), red blood cell (RBC), hemoglobin, hematocrit, platelet count, mean corpuscular hemoglobin (MCH), mean corpuscular hemoglobin concentration (MCHC), mean corpuscular volume (MCV) Differential WBC count: neutrophils, monocytes, lymphocytes, eosinophils, basophils, atypical lymphocytes
Coagulation	prothrombin time (PT), activated partial thromboplastin (aPTT), international normalized ratio (INR)
Complement	CH50, C3, C4
Clinical Chemistry Panel	Renal: Serum sodium, potassium, chloride, carbon dioxide (CO 2 ), calcium, phosphate, creatinine, blood urea nitrogen, uric acid
	Endocrine: serum glucose, free thyroxine (free T 4 ), total or free triiodothyronine (total or free T 3 ), thyroid stimulating hormone (TSH)
	Liver: serum alanine aminotransferase (ALT), aspartate aminotransferase (AST), lactate dehydrogenase (LDH), alkaline phosphatase, albumin, total protein, total bilirubin
	Lipids: Serum cholesterol, triglycerides
Urinalysis	Dipstick testing (urinalysis and microscopy will be conducted only if dipstick results are abnormal)

Laboratory data will be presented in International System of Units (SI) and in the order presented in the protocol. Laboratory grades will be reported using the CTCAE v4.03 (see [Appendix Section 16.5](#)); ungraded laboratory assessments will be reported using normal ranges.

Laboratory tests that are graded for both low and high abnormal values will have both values summarized separately with directions (hyper- or hypo-) labeled accordingly.

Separate summary tables of the observed and change from baseline values for hematology, chemistry, coagulation, and complement laboratory tests will be produced.

Definition of the baseline assessment is in [Section 8.2.5](#).

The denominator in percentage calculations at each scheduled visit will be based on the number of subjects with a non-missing value at each visit.

Idera Pharmaceuticals, Inc.  
Statistical Analysis Plan  
Protocol Number: 2125-MEL-301

---

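### SAP 8.2.9 keeps the latest repeat at a scheduled visit, so a retest prompted by an abnormal laboratory value can displace that value from by-visit summaries; complement has no worst-case table to catch it

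*SAP*

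**What the plan says.** **Record selection (SAP 8.2.9).** For repeats on different days reported under one scheduled assessment, "then the latest assessment for that scheduled assessment will be analyzed". For repeats on the same date and planned time, "then the worst-case result will be analyzed". Data keep the nominal visit under which they were reported ("no visit windows will be applied during dataset creation"). On unscheduled values: "Unscheduled data will only be included in summaries of worst-case (highest and/or lowest) post-baseline assessments". All values are listed.

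**What prompts repeats.** Protocol 9.3.4 sets ANC, platelet and non-hematologic toxicity criteria for each dose of study drug. If they are not met, "dosing will be delayed, and the subject should be re-evaluated within 48 to 72 hours". Section 9.3.4.1 has the same re-evaluation step for ipilimumab. For a complement drop of at least 50%, or to below the lower limit of normal, Protocol 9.3.4.2 says: "The patients should return to the clinic to have another serum sample drawn".

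**What is produced.** SAP 11.8: "Separate summary tables of the observed and change from baseline values for hematology, chemistry, coagulation, and complement laboratory tests will be produced". It adds boxplots with outliers at each scheduled visit for hematology and chemistry, which SAP 16.2 lists for the IDMC as well as for the ORR and final analyses. Worst-case shift tables are planned for CTCAE-graded hematology and chemistry tests and for a selected list of tests against the normal range.

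**The concern.** A latest-value rule is harmless when repeats happen for reasons unrelated to the result. Here the protocol asks for a repeat because the result was abnormal. A re-evaluation 48 to 72 hours later falls on a different day, so if it is filed under the same visit the latest-value rule applies. Dosing goes ahead only once the criteria are met, so for a subject who is then dosed the retained value tends to be the one that passed. Selection then depends on the outcome being summarised.

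The SAP is also inconsistent on this point: two abnormal-then-normal draws on one day keep the abnormal value, while the same two draws on different days lose it from the by-visit summary. No reason is given for the difference.

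At stake is how faithfully the by-visit safety displays show low counts, raised chemistry values and complement drops. The primary analyses of ORR and OS are not affected.

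**Working it through.** The plan states no figure for this rule, so there is nothing to reproduce. The check has three parts.

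**1. What survives, by how the site files the two values.**

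| Triggering value filed as | Retest filed as | By-visit summary uses | Triggering value still appears in |
|---|---|---|---|
| Scheduled visit | Same scheduled visit | Retest | Worst-case tables (if superseded values count) and listings |
| Scheduled visit | Unscheduled | Triggering value | By-visit summary, worst-case tables, listings |
| Unscheduled | Scheduled visit | Retest | Worst-case tables and listings |

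The documents do not say which filing applies. The plus or minus 3-day assessment window does not settle it, because SAP 8.2.9 applies no windows.

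**2. Whether a worst-case table exists.**
- ANC and platelets are CTCAE-graded (SAP 16.5) and have worst-case shifts using scheduled and unscheduled data (SAP 7 and 11.8).
- Graded chemistry tests are covered in the same way.
- CH50, C3 and C4 are in neither the CTCAE table nor the SAP 11.8 normal-range shift list. Their only planned summary is change from baseline.
- Protocol 15.5 calls for shifts to the worst case on study for continuous laboratory values, judged against the normal range when CTCAE has no grade. SAP Section 5 declares no differences from the protocol.

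For complement, rows 1 and 3 of the table therefore leave the triggering value in listings only.

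**3. Illustrative size for ANC against the 1.5 x10^9/L criterion.** All rates are assumptions. Let f be the share of visit values that fail, r the share of those that pass on retest, and q the share of retests filed under the same visit.

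Share shown as failing = f x (1 - q x r)

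With f = 5%:
- q = 1, r = 0.5: 5% x 0.5 = 2.5%
- q = 1, r = 0.9: 5% x 0.1 = 0.5%
- q = 0.5, r = 0.9: 5% x (1 - 0.45) = 2.75%
- q = 0: 5%, no distortion

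A simulation of log-ANC with q = 1 (log-SD 0.45, test-retest correlation 0.3 to 0.8, no recovery trend built in) gave:

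| Failing on first value | Shown after one retest | Shown after retests until pass (up to 7) |
|---|---|---|
| 2% | 0.2-0.9% | 0.0-0.2% |
| 5% | 0.7-2.5% | 0.0-0.7% |
| 10% | 2.2-5.6% | 0.0-2.0% |

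At 5% with one retest, the 5th percentile rises from 1.50 to 1.62-1.72 x10^9/L and the mean from 3.48 to 3.50-3.55. The tail moves; the mean hardly does.

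**The case against.** The other side has several good arguments.

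- **Filing is undocumented.** Nothing is replaced if sites enter retests as unscheduled, and Protocol 10.1.3.6 shows that an Unscheduled Visit form exists. This stands: the effect is conditional.
- **Worst-case tables already cover the main tests.** SAP 7 and 11.8 and Protocol 15.5 all point to every visit being used, clinically significant results are reported as AEs, and listings show everything. This stands for hematology and chemistry. SAP 8.2.9 does not say outright that a superseded scheduled value still counts, but that is an ambiguity to close and not a shown omission.
- **The later value can be worse.** With an evolving toxicity the latest-value rule keeps the worse result, and a subject who never meets the criteria keeps a failing one. This also stands, so the effect is a tendency.
- **The complement redraw differs.** It follows central analysis and sponsor notification, and is meant to confirm the drop. It may be filed separately or be equally low. This limits how often replacement occurs, but does not supply the missing worst-case table.
- **Baseline is also a most-recent value (SAP 8.2.5).** Symmetry has some appeal, but it does not make post-baseline selection neutral when an abnormal result prompts the repeat.

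Two stronger readings are tempting. A reader might infer that QTcF and coagulation summaries are biased as well. Neither is a listed dosing criterion and the documents contain no retest rule for either, so this is unsupported.

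A reader might also infer that the between-arm safety difference is understated, because Arm B has eight dosing visits with a CBC after the first dose and Arm A has three. With 454/2 = 227 per arm, full attendance and f = 5%, that gives 227 x 8 x 0.05 = 90.8 against 227 x 3 x 0.05 = 34.05 failing values. These count opportunities over different numbers of visits. At equal f and equal filing, the expected distortion at any one visit is the same in both arms, and the documents give no failure or retest rates by arm.

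**Conclusion.** The point holds in a limited form. SAP 8.2.9 is a stated rule which, whenever it acts on a retest prompted by an abnormal value and filed under the same visit, tends to remove that value from by-visit summaries. It sits badly with the worst-case rule for same-day repeats.

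For hematology and chemistry the consequence is modest: the by-visit displays, including boxplots that go to the IDMC, may look too normal in the tail, but other planned outputs should hold the value. For complement the gap is more definite, because the protocol mandates a redraw and the SAP omits the worst-case shift that Protocol 15.5 calls for.

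Neither the size nor any difference between arms can be derived from the documents. The percentages above rest on assumed failure rates, assumed test-retest correlation and every retest being filed under the scheduled visit.

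**What to change.** 1. In SAP 8.2.9, use the first valid non-missing value for a scheduled visit in by-visit summaries and treat repeats on later days as unscheduled. Within that first day the existing same-day worst-case rule can stay.
2. State in the same section that every value, including any superseded one, enters the worst-case summaries.
3. Add to SAP 11.8 and the table list in 16.2 a worst-case shift against the normal range for CH50, C3 and C4, to match Protocol 15.5.

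The cost is a few sentences in the SAP, a changed record-selection flag and one extra table. No new data are needed. The downside is that a first sample later judged unreliable would occasionally be kept; excluding samples documented as invalid deals with that.

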### 8.2.10 Strata Used for Analysis

As stated in the protocol, the strata may be collapsed as appropriate with the goal of avoiding strata with too few subjects (the threshold for number of subjects per stratum was pre-defined as 5%). At the time of the finalization of the current version of the SAP, the distribution of subjects across randomization strata was known. The distribution was provided to the Sponsor's medical monitor for review. If a stratum had <5% of subjects, the stratification factor level was combined with another based on clinical judgment. Based on this assessment, stratification factor levels were combined as follows:

1. Metastasis stage M1c and BRAF mutation positive
2. Metastasis stage M1c and BRAF mutation wild type
3. Metastasis stage Other and BRAF mutation positive
4. Metastasis stage Other and BRAF mutation wild type

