The analysis of OS will be performed using a stratified log-rank test controlling for the randomization strata. A sample size of 454 subjects provides 90% power to test the alternative hypothesis of hazard ratio (HR) ≤ 0.677 at an α of 0.005 (one-sided). The HR of 0.677 corresponds to an improvement in the median survival from 11.4 months (the historical control for ipilimumab alone) to 16.9 months with the IMO-2125 + ipilimumab combination.

The OS power calculations are based on log-rank test and assume that the trial will have ~20 months of uniform accrual, an overall study duration up to 56 months, and a 10% drop-out rate. If, under the fallback method, a total alpha of 0.025 is available for the OS significance test, then this test will have 90% power to test the alternative hypothesis of HR ≤ 0.72 at an α of 0.025 (one-sided) which corresponds to an improvement in the median survival from 11.4 months (the historical control for ipilimumab alone) to 15.8 months with the IMO-2125 + ipilimumab combination.

The analysis will be performed when the required number of deaths for the OS analysis (392) is reached, or approximately 36 months after the last subject is randomized, whichever occurs first.

Progression-free survival will be assessed centrally and by investigator using RECIST v1.1 and estimated by the Kaplan-Meier method. Subjects who do not have a PFS event at the time of an analysis, including those who have started new anticancer therapy, withdrawn from the study, or been lost to follow-up without disease progression, will be censored at the date of the last valid disease assessment, defined as the latest assessment at which the subject had a RECIST v1.1 response of CR, PR, or stable disease (SD).

Stratification factors will include duration of prior anti-programmed death receptor-1 (PD-1) therapy (≥ 12 weeks vs < 12 weeks), metastasis stage (M1c vs other), and BRAF mutation status and prior targeted therapy (BRAF wild type, BRAF mutation positive with prior targeted therapy, or BRAF mutation positive with no prior targeted therapy) using block randomization. Targeted therapy is the use of an approved BRAF or MEK inhibitor alone or in combination.

Date of Synopsis: 4 June 2020

Table 1: Schedule of Evaluations – Ipilimumab Alone (Arm A)

Evaluation	Screening ¹	Treatment Period ²						Active F/up ³	Survival F/up ⁴
	Week	1	4	7	10	12	14		
Informed consent ⁵	X								
Inclusion/exclusion	X								
Medical history	X								
ECOG	X	X	X	X	X		X		

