8. STUDY DESIGN

8.1. Overview

This is a randomized Phase 3 global, multi-center, open-label comparison of ipilimumab with and without intratumoral IMO-2125 in subjects with advanced melanoma who had disease progression while on PD-1 directed therapy. Confirmed progression is defined by irRECIST criteria (see Section 20.3). Subjects will be randomized 1:1 to Arm A or B. Randomization is stratified on the duration of prior anti-PD-1 therapy (≥ 12 weeks vs < 12 weeks), metastasis stage (M1c vs other), and BRAF mutation status and prior targeted therapy (BRAF wild type, BRAF mutation positive with prior targeted therapy, or BRAF mutation positive with no prior targeted therapy) using block randomization. Targeted therapy is the use of an approved BRAF or MEK inhibitor alone or in combination. The primary endpoint family of the study comprises OS and ORR.

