15. STATISTICAL ANALYSIS METHODS

15.1. Determination of Sample Size

In this study, ORR and OS comprise a primary endpoint family; both have a priori hypotheses and will be tested for statistical significance. ORR will be tested first followed by OS. The fallback method for the primary endpoint family will be applied to control the study-wise Type I error rate. Under the fallback method, $\alpha_1 = 0.02$ is assigned to the one-sided ORR test and an alpha of 0.005 is saved for the one-sided OS test. If the ORR test is significant at $\alpha_1 = 0.02$, this alpha is unused and will be passed to the OS test as an additional alpha of 0.02, giving a total alpha for the OS test of 0.025.

With 454 subjects randomized with a 1:1 ratio, this test will have 90% statistical power (calculated based on chi-square test) to demonstrate an increase in the ORR from the postulated response of 12% for ipilimumab alone in this setting to 24% for the IMO-2125 + ipilimumab combination, at a 0.02 level of significance.

A sample size of 454 subjects provides 90% power to test the alternative hypothesis of hazard ratio (HR) for OS ≤ 0.677 at an α of 0.005 (one-sided). The HR of 0.677 corresponds to an improvement in the median survival from 11.4 months (the historical control for ipilimumab alone) to 16.9 months with the IMO-2125 + ipilimumab combination. The OS analysis will be performed when 392 deaths are reached.

The OS power calculations are based on log-rank test and assume that the trial will have ~20 months of uniform accrual, an overall study duration up to 56 months, and a 10% drop-out rate. If under the fallback method a total alpha of 0.025 is available for the OS significance test, then this test will have 90% power to test the alternative hypothesis of HR ≤ 0.72 at an α of 0.025 (one-sided) which corresponds to an improvement in the median survival from 11.4 months (the historical control for ipilimumab alone) to 15.8 months with the IMO-2125 + ipilimumab combination.

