#### **9.4 STRATIFICATION FACTORS**

The number of subjects at each stratification factor level at randomization and from the clinical data will be summarized using frequencies and percentages and listed. The summary will be by marginal levels of duration of prior anti-PD-1 therapy ( $\geq 12$  weeks vs  $< 12$  weeks), metastasis stage (M1c vs other), and BRAF mutation status and prior targeted therapy (BRAF wild type [i.e., negative], BRAF mutation positive with prior targeted therapy, or BRAF mutation positive with no prior targeted therapy) as well as the 12 stratification cells. The listing will show the randomized and clinical data stratification levels for each subject.

The duration of anti-PD-1 therapy in weeks will be calculated using start and end dates reported on the Prior Systemic Anticancer Treatment page of the eCRF as (therapy end date – therapy start date + 1)/7 when a therapy is referred to as “PD-1 inhibitor”.

Metastasis stage will be identified from the Baseline Disease Characteristics page of the eCRF as M1c or Other (if not M1c).

Idera Pharmaceuticals, Inc.  
Statistical Analysis Plan  
Protocol Number: 2125-MEL-301

---

BRAF mutation status is reported on the Baseline Disease Characteristics page of the eCRF as negative or positive. Prior targeted therapy for BRAF mutation positive subjects will be identified as the treatment category of prior systemic anticancer therapy of BRAF inhibitor, MEK inhibitor, other targeted therapy, or any combination of these therapies for those subjects with “Positive” BRAF mutation.

[Section 8.2.10](#) describes how the stratification factors are combined. The combined stratification levels will be summarized showing the levels with metastasis stage (M1c or Other) and BRAF mutation status (BRAF wild type or BRAF mutation positive).

The following summaries will be provided:

- Stratification factor levels as randomized
- Stratification factor levels derived from the clinical data
- Stratification factor levels as combined

The following listing will be provided:

- Stratification factor levels

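### SAP 9.4 defines prior targeted therapy more broadly than the protocol, and the SAP leaves two readable stratum sets for the primary tests, one of which omits duration of prior anti-PD-1 therapy

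*SAP*

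**What the plan says.** **Prior targeted therapy.** Protocol 8.1 defines the factor: "Targeted therapy is the use of an approved BRAF or MEK inhibitor alone or in combination". The protocol synopsis, Protocol 15.4.1.2 and SAP section 4 give the same definition. SAP 9.4, which derives the factor from the eCRF for BRAF-positive subjects, counts "BRAF inhibitor, MEK inhibitor, other targeted therapy, or any combination of these therapies". SAP section 5 states that no planned analysis differs from the protocol.

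**Strata.** The protocol synopsis says: "The analysis of OS will be performed using a stratified log-rank test controlling for the randomization strata". It says the same of the CMH test for ORR. Protocol 15.4.1.2 lets strata be collapsed depending on their distribution and leaves the details to the SAP. SAP 8.2.10 sets a 5% threshold, notes that the distribution across randomization strata was already known, and gives the rule: "If a stratum had <5% of subjects, the stratification factor level was combined with another based on clinical judgment". The outcome is four strata, M1c or other by BRAF positive or wild type. SAP 10.1.1 stratifies the ORR test by the randomized strata and refers to 9.4. That section lists the 12 randomization cells and also points to the combined levels of 8.2.10. SAP 10.1.3 gives the OS log-rank test and the Cox hazard ratio the same strata as ORR.

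**The concern.** The 9.4 derivation contradicts the factor it is meant to reproduce. A BRAF-positive subject whose only such prior treatment falls in the added category would be recorded as having had prior targeted therapy, contrary to the protocol. That would create apparent disagreement between the strata as randomized and the strata from clinical data.

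In 8.2.10 the trigger is a small cell, but the remedy merges whole factor levels. Duration of prior anti-PD-1 therapy, one of the three randomization factors, therefore disappears from large cells as well as small ones. If duration is strongly prognostic for survival, a test that ignores it gives up some of the precision that stratified randomization was meant to provide. Because 10.1.1 cites 9.4 rather than 8.2.10, two programmers could also run the sole ORR test, and with it OS, on different strata.

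**Working it through.** **1. The plan's own figures.** Inputs from Protocol 15.1: a one-sided alpha of 0.02 "is assigned to the one-sided ORR test and an alpha of 0.005 is saved for the one-sided OS test"; "With 454 subjects randomized with a 1:1 ratio, this test will have 90% statistical power (calculated based on chi-square test"); an increase "from the postulated response of 12% for ipilimumab alone in this setting to 24% for the IMO-2125 + ipilimumab combination"; and for OS, "The HR of 0.677 corresponds to an improvement in the median survival from 11.4 months", with 392 deaths.

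- ORR, 227 per arm, pooled rate 0.18: z = [0.12√227 − 2.054√(2×0.18×0.82)] / √(0.12×0.88 + 0.24×0.76) = (1.808 − 1.116)/0.537 = 1.29, so power is 90.1%.
- OS at HR 0.677, alpha 0.005 (Schoenfeld): 4(2.576 + 1.282)²/(ln 0.677)² gives 392 deaths after rounding up; power at 392 is 90.1%.
- OS at HR 0.72, alpha 0.025: 390 deaths; power at 392 is 90.2%.

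The stated figures reproduce. They use an unstratified chi-square test and a log-rank test with no credit for stratification, so collapsing strata does not undermine them.

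**2. Is collapsing plausible?** 5% of 454 is 22.7 subjects, and the average of 12 cells is 454/12 = 37.8. Cells below 5% are likely. The cell counts are not shown, so whether the whole duration factor had to go cannot be checked. SAP 9.4 promises a summary of the combined levels, but the table list in SAP 16.2 has only 14.1.7.1 (as randomized) and 14.1.7.2 (clinical data).

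**3. Effect on OS power.** The documents give neither the share of subjects with under 12 weeks of prior therapy nor its prognostic effect, so both are assumed over a range. Simulation: 454 subjects, blocked 1:1 within 12 cells, 20-month uniform accrual, analysis at the 392nd death, no drop-out, M1c share 50% with hazard ratio 1.5, BRAF split 50/30/20%, 3,000 runs per row (Monte Carlo SE about 0.6 points per power). Treatment HR 0.677, alpha 0.005; differences are from unrounded values:

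| Share <12 weeks | Duration HR | 12 strata | 4 strata | Gain from keeping the 12 cells (points) |
|---|---|---|---|---|
| 15% | 1.0 | 89.2% | 90.0% | −0.8 |
| 15% | 1.3 | 88.1% | 89.3% | −1.2 |
| 15% | 1.6 | 87.7% | 87.6% | +0.1 |
| 15% | 2.0 | 87.8% | 87.0% | +0.8 |
| 15% | 2.5 | 88.1% | 86.0% | +2.2 |
| 30% | 1.0 | 89.1% | 90.2% | −1.2 |
| 30% | 1.3 | 87.9% | 88.8% | −0.9 |
| 30% | 1.6 | 88.0% | 88.1% | −0.1 |
| 30% | 2.0 | 88.3% | 85.3% | +3.0 |
| 30% | 2.5 | 87.5% | 82.9% | +4.6 |

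At HR 0.72, alpha 0.025 and a 30% share, 12 versus 4 strata give 88.8% vs 89.2% (duration HR 1.0), 88.7% vs 88.8% (1.5) and 88.6% vs 86.2% (2.0).

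A second simulation compared eight strata (the four split by duration) with four, using 2,500 runs, M1c 60%, BRAF 55/30/15%, and analysis at 392 deaths or month 56. At duration HR 2.0 it gave 88.2% vs 85.5% (25% share) and 88.3% vs 84.9% (35% share). At HR 1.5 it gave 88.3% vs 88.1%, and at 1.0, 88.4% vs 89.2%. The pattern is the same.

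**4. Effect on ORR power.** With 4,000 runs per scenario, shares of 15% and 30%, and odds ratios for short duration from 1.0 to 0.3, the 12-strata and 4-strata CMH tests never differ by more than 0.5 points (largest: 91.4% vs 90.9%).

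**5. Where the definition reaches.** It feeds the clinical-data strata table (14.1.7.2) and the strata listing (16.2.1.3.1). Subgroup tables 14.2.1.4.2 and 14.2.3.4.2 name prior targeted therapy in their titles, but SAP 10.1.6 defines that subgroup as BRAF wild type versus positive only, so their use of the derivation is possible, not stated. BRAF status is a separate eCRF item. The four strata do not use the label.

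**The case against.** The collapse is authorised by Protocol 15.4.1.2, and 8.2.10 states its aim, threshold and result. Duration is not abandoned: SAP 10.1.6 keeps it as a subgroup for ORR and OS. For a weak factor, fewer strata give slightly more OS power, and nothing in the documents shows that duration is strongly prognostic. All of this stands, and it is why the point concerns clarity and a modest protective change rather than an error in the tests.

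A fixed eight-strata scheme is also not clearly better by the SAP's own rule. With M1c 60%, BRAF-positive 45% and a 25% share (all assumed), the cell for other stage, BRAF positive and short duration is 0.40 × 0.45 × 0.25 = 4.5%, about 20 of 454 subjects and under the 22.7 threshold. That is a reason to merge individual sparse cells rather than impose eight strata.

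Finally, re-choosing strata after their distribution is known adds another data-informed step in an open-label trial. That is fair, but the choice in 8.2.10 was made under the same conditions, and a stated merging order on pooled counts limits the risk.

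**Conclusion.** Two textual defects stand; both are minor.

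(1) SAP 9.4 contradicts the protocol and SAP section 4 on prior targeted therapy. A reader might infer that BRAF-positive subjects are misclassified in the primary analysis. The documents do not support that: BRAF status is unaffected, and only the with/without label within BRAF-positive subjects can move. If the four strata apply, no test uses the label. If the randomized strata apply, the levels come from randomization, not from the eCRF derivation. The number of subjects affected is unknown.

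(2) The strata for the primary tests are ambiguous, and the 8.2.10 set omits duration. A reader might infer that duration is lost from every stratified analysis and that power falls below plan. Neither follows: 10.1.1 can be read as keeping the 12 cells, and the planned 90% takes no credit for stratification. Dropping duration has almost no effect on ORR. For OS at HR 0.677 it costs about 3 to 5 points if duration has a hazard ratio of about 2 to 2.5 at a 30% share. At a 15% share the cost is at most about 2 points. If duration is weak or not prognostic, keeping it costs about 1 point. These sizes rest on the assumed shares and prognostic effects above.

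**What to change.** - In SAP 9.4, delete the added category and restore the protocol definition, including that the inhibitor be approved.
- Before unblinding, which in this open-label trial means before efficacy is compared by arm, name one stratum set in 8.2.10, 10.1.1 and 10.1.3, with matching cross-references.
- Keep duration by merging only individual cells under 5% into a neighbouring cell, in a stated order, using counts pooled over arms, and report those counts. At minimum, add a stratified OS sensitivity analysis that retains duration; the stratification sensitivity analysis in 10.1.4 is unstratified and does not serve this purpose.

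The cost is SAP wording and minor programming, plus about 1 point of OS power if duration proves not to be prognostic. The cell-merging scheme was not itself simulated. Since it keeps duration in the larger cells, it should behave much like the 8- and 12-strata tests.
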